## Study Design

The **pilot study** consists of two research scenarios, in which two different sequences of the interventions taking the form of the pre-programmed tilt and LBNP profiles are to be investigated. The two study scenarios are designed based on the knowledge and experience of the investigators in the fields of examinations of military pilots in real and simulated conditions [17],[18].

**Scenario I** is designed to initially verify the potential impact of the prototype system on the human body. For this purpose, only basic tilt and LBNP stimuli of relatively slowly increasing intensities will be used, and the group of subjects will include only subjects with flight experience. Up to 20 PAFA cadets shortly before graduation, including women and men, will

be involved in the pilot study (experimental arm 1). The subjects will be healthy, aged between 20 and 30 years old. Scenario I will take almost 24 min.

**Scenario II** is to compare subjects with and without flight experience using rapid tilt and LBNP stimuli as well as a push-pull stimulus. Up to 30 subjects including up to 15 pilots, i.e., flight school adepts shortly after graduation and/or PAFA cadets shortly before graduation, and up to 15 students of the Aviation High School in Dęblin, Poland, including women and men will be involved in the study (experimental arm 2). The subjects will be healthy, aged between 18 and 30 years old. The students of the Aviation High School will participate in the study as a reference group, without flight experience. Scenario II will take 16 min.

## Methodology

[figure not shown]
### *Prototype system*

The prototype of the ORTHO-LBNP system comprises a tilt table, LBNP chamber and medical monitoring subsystem.

#### Tilt table

The tilt table is placed on two axes terminated on both sides with guide blocks. One of the axes cooperates with a horizontal rail, whereas the other is associated with a vertical rail. The vertically moved guide blocks are driven by a rotary engine, and the horizontally moved guide blocks support the tilt table. The tilt table and thus the subject move around a variable axis of rotation. As shown in Fig. 1, the subject's body slidingly moves in the head-to-feet axis while changing mainly the level of the upper part of the body, both in HUT and HDT tests. Trajectories of three human body characteristic points, i.e., head, waist and feet, during HUT and HDT tests are illustrated by the red and blue solid lines, respectively. Additionally, displacements of the guide blocks on the horizontal and vertical rails are marked with the white and black dotted lines, respectively. Such a movement of the subject lying on the tilt table can, to some extent, simulate flight conditions at a relatively low technical complexity and average costs. This drive subsystem has been registered in the Patent Office of the Republic of Poland [19]. The tilt table meets the following requirements:

- range of tilt angles:  $-45^{\circ}$  to  $+80^{\circ}$ ,
- rate of tilt changes: up to  $45^{\circ}/s$ .

[figure not shown]
**Fig. 1. Trajectories of the body on the tilt table during (a) HUT and (b) HDT tests.**

#### LBNP chamber

[figure not shown]
Initially, we considered the use of a buffer tank between the underpressure chamber and a compressor or vacuum pump to generate negative pressure, as shown in Fig. 2 (dotted line). This required applying controllable valves between the buffer tank and the underpressure

chamber, and a safety valve to reduce pressure in the tank. The compressor was to achieve a much greater negative pressure in the buffer tank than required in the underpressure chamber. In this way a low-flow compressor could be used to reduce pressure in the chamber at the required change rate. Nevertheless, the constructors decided to use only elements that meet the definition of low-pressure equipment according to Directive 2014/68/EU relating to the making available on the market of pressure equipment. Although this required the use of a high-flow compressor to achieve an appropriate pressure dynamics in the chamber, the subsystem for generating underpressure was simplified by eliminating the buffer tank (Fig. 2, solid line). Additionally, the maximum negative pressure achieved by the compressor can be lower than that in the case of a compressor operating in the configuration with the buffer tank. The LBNP chamber is based on an aluminium frame with thermoformed polycarbonate sheet. As a result of numerical simulations, the maps of equivalent stresses and total displacements for particular segments of the chamber, shown in Fig. 3, were obtained. The LBNP chamber meets the requirements as follows:

- range of generated underpressure: 0 to -100 mmHg,
- rate of underpressure changes: up to 20 mmHg/s.

**Fig. 2. Pneumatic subsystem for generating underpressure in the LBNP chamber.**

**Fig. 3. Strength analysis of the LBNP chamber.**

[figure not shown]
The tilt table and LBNP chamber underwent tests for compatibility with the harmonised standards in regards to machinery Directive 2006/42/EC, and hence these two mechanical subsystems have been CE marked. Moreover, the safety of the prototype system has been confirmed by the positive results of laboratory tests carried out with respect to Directive 93/42/EEC concerning medical devices.

### Physiological monitoring

A subsystem for monitoring physiological parameters in subjects undergoing tilt and underpressure tests is necessary to carry out examinations safely and to classify subjects

reliably. The constructors decided to build their own measurement subsystem where all the medical recorders in the form of modules were integrated in electromagnetically (EM) shielded enclosures to which the wires from the electrodes and sensors located on the subject's body were connected as in modern operating tables. Fig. 4 (a) shows the general configuration of the subsystem that consists of modules for the following types of diagnostics: ECG, pulse oximetry (POx), electromyography (EMG), skin conductance level (SCL), NIBP, body temperature (TEMP), impedance reography (REO), electroencefalography (EEG), capnography (CAPNO), near infrared spectroscopy (NIRS), and continuous non-invasive arterial pressure (CNAP). The modules for measuring ECG, EMG, SCL, TEMP, REO, and EEG were developed entirely by the engineering team, whereas the POx (WW3711 by Smith Medical), NIBP (Advantage Mini by SunTech Medical), CAPNO (miniMediCO2 by Oridion Medical), CNAP (CNAP by CNSystems Medizintechnik AG), and NIRS (7610 OEM by Nonin) modules were built on the basis of commercially available certified OEM solutions. In addition to the commercial off-the-shelf 2-channel NIRS device, we used an in-house-designed 6-channel module to record oxygenation changes in the left and right frontal lobe, motor cortex, and visual cortex. All the modules were connected to the operator's station and the control module via the data hub. The module set and data hub were closed in a propacPRO series EM shielded enclosure by Schroff (Fig. 4 (b)), but the in-house-designed NIRS module was enclosed separately in another propacPRO housing due to its size (Fig. 4 (c)). The medical monitoring subsystem has been certified with a CE marking indicating conformity with the standards harmonised with Directive 93/42/EEC.

**Fig. 4. Medical monitoring subsystem: the (a) block diagram, (b) main module box by the Institute of Medical Technology and Equipment, Poland, (c) in-house-designed NIRS module box by the Nałęcz Institute of Biocybernetics and Biomedical Engineering of the Polish Academy of Sciences.**

[figure not shown]
### Software

A computer application for controlling the tilt table and LBNP chamber, as well as receiving, analysing and presenting data from the medical modules during examination was developed during construction of the prototype system. The software runs on the Microsoft .Net Framework 4.0 platform. It was prepared in the C # language using the Visual Studio environment. The source code was developed according to the applicable design principles and software engineering principles. A set of tests for the individual software units and integration tests were also prepared. Similar to the medical monitoring subsystem, the computer

application complies with the requirements of the standards harmonised with Directive 93/42/EEC and has been certified with a CE marking.

The prototype system developed at technology readiness level 9 was deployed in a room with medical approvals, and prepared for pilot-based studies. A photograph of a subject being examined with the prototype of the ORTHO-LBNP system is shown in Fig. 5 (a). A neoprene skirt similar to those used in kayak sports was applied to seal the space between the subject and the edge of the LBNP chamber. The sealing skirt was customised by the manufacturer so that two ropes can be attached to it to prevent the skirt from sliding off the hips when negative pressure is applied. The ropes were fastened on the other side to the stands mounted at the head of the table. For a continuous recording of arterial pressure acquired from the subject's finger at the heart level, an adjustable handrest was designed and installed on top of the LBNP chamber.

A unique feature of the prototype system is the ability to carry out experiments with a saddle on which the patient is placed for minimising the impact of the footboard (Fig. 5 (b)) on the subject's legs. In this way some researchers tried to reduce the leg muscle tension and weaken the blood pushing out toward the upper part of the body [20]-[22]. Thus the seat may intensify the effect of blood pooling in the lower extremities and we decided that the prototype system would be equipped with a removable saddle as an option for research applications, as shown in Fig. 5 (c).

[figure not shown]

**Fig. 5. Photographs of the prototype system: a (a) subject during an examination, the (b) open LBNP chamber with the footboard, (c) optionally mounted saddle.**

## Research scenarios

### Scenario I

[figure not shown]
Scenario I will be composed of seven phases, shown in Fig. 6, which can be characterised as: (1) 300-s check before the stimuli, (2) LBNP is applied stepwise with 11.1 mmHg/15 s decrement to -100 mmHg, and then this value is sustained for 120 s, (3) 180-second phase of rest between stimuli, (4) 75°-HUT (5°/s) for 120 s after a 15-s reversing of the gravity vector (-30°), (5) 180-second phase of rest between stimuli, (6) 75°-HUT (5°/s) accompanied by an exposure to an LBNP of -60 mmHg increased linearly by -4 mmHg/s, and then this value is sustained for 120 s during HUT, and (7) 120-s check after the stimuli.

**Fig. 6. Tilt and LBNP profiles in 24-min Scenario I.**

### Scenario II

Scenario II will be composed of seven phases, shown in Fig. 7, which can be characterised as: (1) 120-s check before the stimuli, (2) 75°-HUT (45°/s) for 60 s after a 3-s reversing of the gravity vector (-30°), (3) 180-second phase of rest between stimuli, (4) LBNP decreases linearly by -20 mmHg/s to -100 mmHg, and then this value is sustained for 60 s, (5) 180-second phase of rest between stimuli, (6) push-pull, i.e.,  $3 \times 75^\circ$ -HUT (45°/s) preceded by -30°-HDT (45°/s) and accompanied by an exposure to an LBNP of -60 mmHg decreased linearly by -20 mmHg/s, and then this value is sustained for 30 s during HUT, and (7) 120-s check after the stimuli.

**Fig. 7. Tilt and LBNP profiles in 16-min Scenario II.**

The pilot study will be carried out in an isolated room in the presence of a physician (physiologist), a paramedic and an ORTHO-LBNP system operator. The paramedic will prepare the subject for the study by placing on his/her body electrodes and measuring sensors that will be removed after completion of the study. The subject will be asked to close his/her eyes during the tests and to place his/her hands on the rest. In order to cause the least disturbance, no conversation will be held with the subject. Only if disturbing symptoms will occur, will the subject immediately report this to the personnel. The physician will systematically be observing the subject's cardiogram, his/her HR, CNAP wave, and systolic and diastolic blood pressure (SBP and DBP, respectively) in comparison with the changing tilt of the table and negative pressure in the chamber. Any time, at the request of the subject or on the instruction of the doctor, the operator will interrupt the tests. The tilt table then will return to the Trendelenburg position if interruption occur during HUT and/or LBNP stimuli, or horizontal position if interruption occur during HDT stimulus. At the same time atmospheric pressure will be resumed in the chamber.

## Safety Considerations

The subjects will be informed of possible presyncope symptoms that may occur during the tilt and/or LBNP exposure, with an emphasis on the prompt notification of any symptoms. Prior to the exposure, a shortened medical survey will be performed, including a subjective examination for possible contraindications to the exposure, and a physical examination, i.e., RR and HR measurements in sitting and standing positions. Once the subject is placed in the LBNP chamber, their resting ECG as well as SBP and DBP will be assessed.

Both tilt and LBNP tests are relatively safe, but complications in the form of ventricular arrhythmias or asystole are known. Therefore, at the time of the study, the presence of trained medical personnel, consisting of a physician and paramedic, shall be provided. The following rescue equipment will be available:

1. Ambu self-inflating bag with connector to supply oxygen.
2. Oxygen cylinder with reducer. Check the filling status before exposure!
3. Automatic defibrillator. Check the battery charge before exposure!
4. Anti-shock kit in accordance with the Executive Regulation of the Minister of Health of 24 September 2013 on the guaranteed benefits in the area of primary healthcare (Journal of Laws, 2013, item 1248) and Law of 6 September 2001 - Pharmaceutical Law (Journal of Laws, 45, 2008, item 271) with amendments. The detailed composition of the anti-shock kit is presented in **Appendix A** to this research protocol.

If presyncope syndromes are present, immediately stop the HUT and/or LBNP exposition and move the tilt table to the Trendelenburg position (tilt angle of  $-16^{\circ}$ ). There is a difference in the way of handling push-pull simulations. The procedure depends on the study phase. For  $+G_z$  exposures, i.e., HUT and/or LBNP, immediately stop the LBNP exposure (if used) and move the tilt table to the Trendelenburg position. In the event of any feeling of discomfort by the subject during  $-G_z$  exposures, i.e., HTD, the orthostatic exposition should be discontinued and returned to the horizontal position of the tilt table (tilt angle of  $0^{\circ}$ ).

In case of asystole or ventricular arrhythmias in the form of ventricular tachycardia or ventricular fibrillation, the resuscitation procedure should be implemented in accordance with the adult advanced life support (ALC) algorithm:

1. Check whether the victim reacts, whether breathing or not, or does not have single sighs.

2. Inform the MIAM resuscitation team at the Intensive Care Unit - [contact].
3. Start a cardiopulmonary resuscitation according to scheme 30:2, i.e., provide 30 chest compressions, followed by two breaths.
4. Supply oxygen to the self-inflating bag used for resuscitation.
5. Connect the defibrillator/monitor, minimise resuscitation intervals.
6. Rate the heart rhythm.
7. Perform defibrillation if there is a ventricular fibrillation (VF) or ventricular tachycardia (VT) without pulse. Follow the procedure given by the automatic defibrillator.
8. Immediately take cardiopulmonary resuscitation (CPR) for 2 minutes, minimise resuscitation intervals.
9. Rate the heart rhythm, continue ALC.

## Follow-Up

After the study, on the same day, it is advisable not to drive or fly an aircraft.

## Data Management

MIAM is both a research institute and medical centre, where data management and information security are provided in accordance with the ISO IEC 27001 standard. A copy of the certificate is included as **Appendix B**.

## Statistical Analysis Plan

The statistical analysis of the results will be performed in two aspects:

1. Differentiation of the study phases (scenario I).  
The statistical analysis will be directed toward estimating how separate tilt and LBNP stimuli and the complex stimulus affect basic physiological parameters, i.e., HR, inter-beat interval (IBI), SBP, DBP, mean arterial pressure (MAP), stroke volume (SV), cardiac output (CO), left ventricular ejection time (LVET), rate pressure product (RPP), and total peripheral resistance (TPR), calculated using the ECG and CNAP signals. The mean values of the individual parameters for the test group (experimental arm 1), along with standard deviations and standard errors, will be determined for each experiment phase, and their changes will be described in relation to the check before the stimuli (phase 1). Finally, significances of these changes will be shown.
2. Differentiation of the study phases and differentiation of subjects with various level of flight experience (scenario II).  
The statistical analysis will be directed toward estimating how separate tilt and LBNP stimuli and the combined stimulus as well as the level of flight experience affect HR, IBI, SBP, DBP, MAP, SV, CO, LVET, RPP, and TPR, calculated using the ECG and CNAP signals, base transthoracic impedance ( $Z0\_T$ ), first derivative of transthoracic impedance ( $dZ/dt\_T$ ), base trancephalic impedance ( $Z0\_H$ ), and first derivative of trancephalic impedance ( $dZ/dt\_H$ ), calculated using the REO signals, changes in oxygenated haemoglobin ( $\Delta C\_HbO2$ ), changes in deoxygenated haemoglobin ( $\Delta C\_Hb$ ), and changes in total haemoglobin ( $\Delta C\_tot$ ), calculated using NIRS signals. The mean values of the

individual parameters for the test group (experimental arm 2), along with standard deviations and standard errors, will be determined for each experiment phase, and their changes will be described in relation to the initial level in phase 1. Additionally, descriptive statistics of the above-mentioned physiological parameters obtained by the subjects with flight experience in relation to the parameters obtained by the subjects without flight experience, will be performed. Finally, significances of changes in physiological parameters along with the subsequent phase of the research work and the level of flight experience will be presented.

We do not have a preferred statistical method at the time of preparing the research protocol and planning the pilot study. However, we expect negative results of the normal distribution test and hence the use of nonparametric statistical tests, e.g., the Friedman-Kendall analysis of variance for multiple dependent samples. A more detailed description of the used statistical analysis and level of significance will be included in publications, and the PRS record will be complemented with the results.

## Quality Assurance

MIAM has a quality management certificate based on the ISO 9001:2008 and AQAP 2120:2009 requirements. Moreover, high quality of the research carried out at the institute has been confirmed by the certificates issued by the US Air Force in the following areas:

- aerospace physiology and centrifuge training program,
- acceleration physiology and centrifuge training program.

Copies of the certificates are included as **Appendix B**.

## Expected Outcomes of the Study

During the implementation of both research scenarios, all signals/parameters that can be acquired by the medical monitoring subsystem will be recorded. However, in scenario I the main emphasis will be placed on the analysis of basic physiological parameters, i.e., HR, inter-beat interval (IBI), SBP, DBP, mean arterial pressure (MAP), stroke volume (SV), cardiac output (CO), left ventricular ejection time (LVET), rate pressure product (RPP), and total peripheral resistance (TPR), calculated using the ECG and CNAP signals. The latest literature shows that the analysis of basic physiological parameters, e.g., heart rhythm and blood pressure, enables for predicting orthostatic hypotension [23] and reveals precursory signs of syncope [24]. Our intention is to verify the behaviour of a group of cadets experiencing accelerations on a regular basis who are subject to tests in a device of a novel design. We expect that a stronger stimulus will cause greater changes in the values of the analysed physiological parameters. Among the stimuli used, the strongest one should be HUT accompanied by LBNP. The analysis should indicate these physiological parameters that should be taken into account in the development of an orthostatic tolerance index (OTI).

The results of scenario II will be focused not only on the impact of the stimuli, but will also be analysed in terms of the distinguishing of subjects with different level of flight experience and quantifying an examined person's propensity to endure gravitational stimuli. Both analysis of basic physiological parameters as well as analysis of indices determining the level of oxygenation of brain areas acquired with the in-house-designed NIRS module will be

performed. It is expected that greater changes in brain oxygenation indices will be seen in the subjects without flight experience than in active pilots that have undergone a training improving their G-tolerance.

We anticipate that new indicators will be proposed to enable an objective assessment of the predispositions to pursue a military pilot career. Finally, this should make the selection procedures in military aviation easier.

At least two manuscripts, one containing the results of scenario I, the other containing the results of scenario II, will be submitted for publication.

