## Study goals and objectives

The objectives of the pilot study can be summarised as follows:

1. Testing the prototype device with participation of humans, where the result measures relate both to feasibility and health outcomes.
2. Checking the system dynamics and verifying how faithfully the system maps the pre-programmed tilt and LBNP profiles.
3. Verifying the signal quality and analysing changes in basic physiological parameters when applying a sequence of the pre-programmed tilt and LBNP profiles.
4. Verifying if new indicators can be proposed for an objectivised assessment of the physiological predispositions of candidates for military aviation.

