## **Dissemination of Results and Publication Policy**

The results will be first reported via the National Centre of Research and Development, Poland, to the Ministry of National Defence, Poland. The Ministry will decide whether to implement the ORTHO-LBNP system into the selection process of candidates for military pilots.

The publications will be prepared under the leadership of the PI. The PI decides on the author lists. Only persons who gave the conception of the prototype system, modelled the tilt table and LBNP chamber, designed and constructed the prototype system, coordinated certification procedures, programmed the tilt and LBNP profiles, designed the experimental protocol, coordinated the pilot study, processed data for analysis, analysed and verified data, and interpreted the results, can be included on the author lists. The person who contributes the most to the preparation of the manuscript will be its first author. If the PI is not the author of the largest contribution, he will be acknowledged as the last author of the article.

All authors will review the manuscripts and accept their final version.

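### Scenario II aims to distinguish subjects and support indicators for candidates, but the SAP plans only group summaries and significances, which do not show how well a parameter separates individuals

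*Combined protocol and SAP*

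**What the plan says.** All references are to the combined protocol and SAP.

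- **Aims.** Expected Outcomes of the Study says scenario II results "will also be analysed in terms of the distinguishing of subjects with different level of flight experience" and adds a second aim, "quantifying an examined person's propensity to endure gravitational stimuli". It then anticipates that "new indicators will be proposed to enable an objective assessment of the predispositions to pursue a military pilot career". Objective 4 in Study goals and objectives is more cautious: "Verifying if new indicators can be proposed for an objectivised assessment of the physiological predispositions of candidates for military aviation".
- **Use.** Dissemination of Results and Publication Policy states: "The Ministry will decide whether to implement the ORTHO-LBNP system into the selection process of candidates for military pilots".
- **Planned output.** Statistical Analysis Plan, aspect 2, covers phase means with standard deviations and standard errors, changes from phase 1, descriptive statistics of experienced against inexperienced subjects, and finally "significances of changes in physiological parameters along with the subsequent phase of the research work and the level of flight experience". The test and the significance level are left to the publications, and nonparametric tests are expected.
- **Size.** Study Design gives "Up to 30 subjects including up to 15 pilots" and "up to 15 students of the Aviation High School".

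No section names an AUC, sensitivity, specificity, cut-off, classification model, validation step or individual score.

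**The concern.** A significance test on two groups asks whether their distributions differ on average. An indicator used on candidates must answer something else: how often would a single person fall on the wrong side? A parameter can pass the first test and do poorly on the second, because groups with clearly different means can still overlap largely. Changing the test, the level or the multiplicity rule alters which parameters are declared significant. It does not turn a p-value into a measure of separation.

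The results go to a body that decides whether the system enters pilot selection. Under the listed outputs, a weak separator with a small p-value could be put forward as an indicator for individuals, and nothing in the planned report would show the reader how weak it is.

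**Working it through.** The plan gives no power, effect size, significance level or accuracy figure, so there is nothing of its own to reproduce. The check asks how well a parameter separates people when it only just reaches significance.

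**Inputs.** n1 = n2 = 15, the maximum in Study Design. Assumed, because the plan is silent: two-sided 5% level, one parameter at a time, normal groups with equal variance, equal prevalence, cut-off midway between the group means.

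**Step 1, smallest significant difference.** d = t(0.975; 28) × √(1/15 + 1/15) = 2.048 × 0.365 = 0.748.

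**Step 2, separation.**
- AUC = Φ(d/√2) = Φ(0.529) = 0.70.
- Misclassified = Φ(−d/2) = Φ(−0.374) = 35.4%.
- Overlap of the two curves = 2 × Φ(−0.374) = about 71%.

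**Step 3, precision of that AUC (Hanley-McNeil).** At A = 0.70:
- Q1 = 0.70/1.30 = 0.538 and Q2 = 2 × 0.49/1.70 = 0.576.
- SE² = [0.70 × 0.30 + 14 × (0.538 − 0.49) + 14 × (0.576 − 0.49)]/225 = 0.0093, so SE = 0.097.
- 95% CI: 0.70 ± 1.96 × 0.097 = 0.51 to 0.89.

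**Step 4, rank test.** The plan expects non-normal data. The exact Mann-Whitney boundary at 15 + 15 is U = 64 (p = 0.045), so AUC = 1 − 64/225 = 0.716. This value needs no normality. Converted to a normal-model d of 0.81, it gives 34.4% misclassified.

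**Step 5, sensitivity of the 35%**, changing one input at a time:

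| Setting | d | Misclassified |
|---|---|---|
| 15 + 15, one-sided 5% | 0.621 | 37.8% |
| 15 + 15, two-sided 5% | 0.748 | 35.4% |
| 15 + 15, two-sided 1% | 1.009 | 30.7% |
| 15 + 15, two-sided 5%/17 | 1.190 | 27.6% |
| 12 + 12, two-sided 5% | 0.847 | 33.6% |
| 10 + 10, two-sided 5% | 0.940 | 31.9% |
| 8 + 8, two-sided 5% | 1.072 | 29.6% |

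The range is about 28 to 38%. Stricter levels go lower: 5%/51 at 15 + 15 gives d = 3.681 × 0.365 = 1.344 and Φ(−0.672) = 25%. A strict level combined with smaller groups goes lower again (8 + 8 at 5%/17: 18.5%).

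**Step 6, benchmarks.** A true difference detectable with 80% power at 15 + 15 (d = 1.06) still misclassifies 29.8%. An error of 20% needs d = 1.68, and 10% needs d = 2.56. An observed d of 0.748 has a 95% CI of 0 to 1.48, that is, an error anywhere from 50% to 23%.

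**Step 7, number of comparisons.** Aspect 2 lists 10 parameters from ECG and CNAP, 4 from impedance and 3 from NIRS, so 17. Scenario II has three stimulus phases (2, 4 and 6). 17 × 3 = 51, and more if the NIRS channels are analysed separately.

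**The case against.** **Distinguishing may mean comparing groups.** Study Design describes scenario II as a comparison of subjects with and without flight experience, and the SAP applies the word differentiation to phases as well as to subjects. That is a fair reading of the one phrase. It does not cover the aim of quantifying an examined person's propensity, or the indicators for candidates in objective 4 and in Expected Outcomes.

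**It is a pilot.** Objective 4 asks only whether indicators can be proposed, and screening by group difference is a normal first step. This stands, and it limits the weight of the point. A reader might infer that the group comparison is invalid or that the study must validate a classifier; the documents support neither.

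**The plan is open, not restrictive.** Methods are deferred to publication, and means with standard deviations let a reader derive d and an approximate overlap. True, so it would be wrong to say that the plan excludes a measure of separation, or that the Ministry will see nothing but p-values. But no such measure is among the planned outputs, and leaving the test open still leads to significances.

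**The 35% is conditional.** Correct. A reader might also infer that a significant parameter could leave the groups almost fully overlapping. At the 15 + 15 boundary the overlap is about 71%, which is large but not almost complete.

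**An AUC for flight experience does not measure predisposition.** This stands. Expected Outcomes itself links the expected difference in brain oxygenation to training, and the groups also differ in career stage. Even a high AUC would not show who among untrained candidates is suited, so the report must say so.

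**Conclusion.** The point holds as a missing analysis for a stated aim. Scenario II is meant to distinguish subjects and support indicators for candidates, while aspect 2 of the Statistical Analysis Plan lists only group summaries and significances. With 15 + 15 subjects and an assumed two-sided 5% level, a parameter that just reaches significance has an observed AUC of about 0.70 to 0.72. It misclassifies about 35%, given one parameter, equal-variance normality and equal prevalence. The 35% treats the observed difference as the true one and concerns separation by flight experience only. For tolerance to gravitational stimuli the SAP defines no individual outcome, so no accuracy can be worked out. Combining parameters might lower the error, but no combination is planned. The change should be made before the data are analysed.

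**What to change.** **Statistical Analysis Plan, aspect 2.** For each parameter's change from phase 1, in each stimulus phase, report the AUC for experienced against inexperienced subjects, U/(n1 × n2), with a 95% CI beside the significance. State the number of comparisons (at least 51). Give multiplicity-adjusted intervals for any parameter singled out.

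**Expected Outcomes of the Study.**
- Call a parameter distinguishing only if its adjusted lower limit exceeds a value fixed before analysis and clearly above 0.5. At 0.5 the rule would largely restate significance: the just-significant case above has an unadjusted lower limit of 0.51.
- Report all other parameters as group differences only.
- Use leave-one-out validation for any combination of parameters.
- State that the AUC measures separation of pilots and cadets from high-school students, not predisposition or tolerance. Any indicator reported to the Ministry is then a candidate that needs validation.

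**Cost.** SAP wording and a few lines of code on data already collected; no extra subjects. The downside is a more modest claim. With a Bonferroni adjustment over 51 comparisons (z = 3.30), an observed AUC of 0.80 (Hanley-McNeil SE 0.082) has a lower limit of 0.80 − 3.30 × 0.082 = 0.53, so few or no parameters may qualify with 30 subjects. At that level a symmetric interval can run past 1 (0.80 + 3.30 × 0.082 = 1.07), so the SAP should name an interval method that stays within 0 to 1.
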